A retrospective cohort data linkage study of patients aged 18 years and above registered in English general practices. This protocol is written following RECORD guidance [12].

Settings Describe the setting, locations, and relevant dates, including periods of recruitment, exposure, follow-up, and data collection.

1205 general practices in England contributing to the QResearch database, which is nationally representative. We defined cohorts during the COVID pandemic as between 24th January 2020 (the date of the first confirmed COVID-19 case in England) and study end (30th June 2021). We defined retrospective comparison cohorts as the 5 years prior to this date (24th January 2015- 23rd January 2020).

Data linkage

The study will include adult patients registered with the QResearch database. Practices must have been contributing to the QResearch database for at least 12 months. For the investigation of associations of pre-existing neuropsychological diseases and treatments (cohort 1) patients must be registered for at least a 12-month period before 24th January 2020. For the investigation of incidence of new neuropsychological diseases (cohort 2) patients must be registered for at least a 12-month period between January 2015 to 2020. The date of study entry is separately defined below for each study cohort.

Patients in QResearch will be linked to: (1) the ICNARC Case Mix Programme (CMP) database, the national clinical database from adult critical care; (2) the Hospital Episode Statistics (HES) data warehouse containing records of all patients admitted to NHS hospitals and Emergency departments in England; (3) the national registry of COVID-19 RT-PCR positive test results from Public Health England (PHE); and (4) Office of National Statistics COVID-19 mortality data, which includes all deaths due to COVID-19 in England. Data linkage will be based primarily on NHS number. For a description of the datasets see Supplemental material S1.

Participants

Give the eligibility criteria, and the sources and methods of selection of participants. Describe methods of follow-up. The methods of study population selection (such as codes or algorithms used to identify subjects) should be listed in detail.

Aim 1.

From the linked dataset, we will extract two cohorts to explore the association between neuropsychological diseases and treatments and hospitalisation, ICU admission or death:

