- Cohort four will include adult patients (aged 18+ on date of hospital admission) discharged alive following a hospital admission including an ICU admission resulting from SARI (defined below) admitted between 24 January 2015 and 23rd January 2020, who were registered in a primary care practice within the QResearch programme before their ICU admission. The cohort will allow comparisons to be made with cohort three. Follow-up will be from the date of discharge. Patients will be censored at the earliest of first occurrence of deregistration from the GP practise, death from other causes, 12 months post discharge from hospital or date of the final data extract from the linked datasets.
- Cohort 5 will include adult patients (aged 18+ on date of hospital admission) discharged alive following a hospital admission including an ICU admission resulting from SARI (defined below) between 24 January 2020 and study end date, who were registered in a primary care practice within the QResearch programme before their ICU admission. It will be used to allow comparison with cohort 3. Patients will be censored at the earliest of first occurrence of deregistration from the GP practice, death from other causes, 12

months post discharge from hospital, or date of the final data extract from the linked datasets.

Variables

Definition of outcomes Aim 1

For cohort one, our primary outcome is the first occurrence of any one of the following:

1. Hospital admission resulting from COVID-19 infection defined as testing positive for SARS-CoV-2 (as recorded in the PHE database) in the 14 days prior to or during a hospital admission period in the HES dataset, or having an ICD10 code U07.01 for confirmed COVID-19 diagnosis in that HES admission record

2. Admission to an ICU resulting from COVID-19 infection which will be defined as patients admitted to an ICU within the ICNARC dataset of COVID-19 admissions.

3.All - cause mortality following COVID-19 infection.

Secondary outcomes are each of the three events defined above, considered separately (i.e. COVID-19 hospital admissions; ICU admission; death).

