- oral steroids

Intensive care stay (Aim 2)

- Length of stay
- Duration of advanced respiratory support (invasive ventilation)
- Use of sedation in the first 24 hours of admission

Effect Modifiers

For aim 1, we assessed these potential confounders by creating directed acyclic graphs (DAG) to determine which variables were likely to be to some extent caused by the presence of prior neuropsychological disorders (as the exposure of interest), and which were not likely to be caused by the presence of prior neuropsychological disorders, but were thought to be independently potential predictors of severe Covid outcomes.

Variables from the above list to be included in the model are all those grouped under: demographics; co-morbidities; lifestyle factors; plus prescription of any immunosuppressants and/or anticoagulants. Other medications (as these are not believed to affect the risk of severe Covid outcomes), and in-hospital factors (length of stay and use of sedation during intensive care admission, as these are outcomes potentially caused by Covid severity) will not be adjusted for.

For aim 2, our exposure of interest is admission to intensive care with SARI (compared to admission to intensive care with SARI. This exposure occurs at a fixed time which is used as the baseline for our time to event analysis in predicting the outcome of interest, and all other variables listed above are measured before this baseline. Therefore (depending on the available sample size and number of events), all the previously listed covariates of interest may be included in our adjusted models.

Data sources

Intensive Care Unit admission data will come from the ICNARC CMP dataset Hospital admission and mortality will come from the HES dataset

All exposures and confounders and neuropsychological outcomes will come from the QResearch database.

COVID-19 infection test status will come from the national registry of COVID-19 RT-PCR positive test results from Public Health England (PHE).

Bias

To limit the possible impact of COVID-19 testing bias (collider bias) we will analyse the entire QResearch eligible population, rather than restricting analysis to only those with a positive COVID-19 test.

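### Cohort 1's death outcome does not say how infection is established, and a COVID-19 death with no positive test and no COVID-19 admission has no stated route into it, although ONS COVID-19 deaths are linked

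*Protocol*

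**What the plan says.** Under Definition of outcomes Aim 1, the cohort 1 primary outcome is the first of three events, and each event is also a secondary outcome.

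- Item 1, hospital admission, accepts a positive PHE test around or during the admission, or "having an ICD10 code U07.01 for confirmed COVID-19 diagnosis in that HES admission record".
- Item 2, ICU admission, is "patients admitted to an ICU within the ICNARC dataset of COVID-19 admissions".
- Item 3, death, is all-"cause mortality following COVID-19 infection". It gives no rule for establishing infection and names no dataset.

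The Data sources section takes infection test status from the PHE registry of positive RT-PCR results. On deaths it says "Hospital admission and mortality will come from the HES dataset". The Data linkage section in Methods describes HES as "containing records of all patients admitted to NHS hospitals and Emergency departments in England". The same section lists as a fourth linked source "Office of National Statistics COVID-19 mortality data, which includes all deaths due to COVID-19 in England".

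The Participants section censors cohort 1 patients at death. The Bias section analyses the whole eligible population to limit testing bias. The Sensitivity analyses section adds an analysis restricted to RNA-confirmed cases.

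**The concern.** Items 1 and 2 have working case definitions, and both can be met without a positive PHE test. Item 3 has none, and the sources named for it may not reach people who died outside hospital without a test. The ONS data that would identify those deaths are linked but given no role in any outcome definition or in Data sources.

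A COVID-19 death that cannot enter the outcome is treated as a censoring. This matters most if it happens more often in one exposure group than another. Dementia is one of the disease classes to be analysed separately, and it is plausible that people with dementia more often died outside hospital without a test. Analysing the whole population controls who enters the cohort. It does not control how a death is classified, so testing can re-enter through outcome ascertainment. At stake are the separate death outcome and, usually to a lesser degree, the primary composite.

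**Working it through.** The protocol gives no figure on this point, so there is none to reproduce.

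**Step 1: follow each kind of COVID-19 death through the text.**

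| Evidence before death | Composite | Separate death outcome |
|---|---|---|
| Positive PHE test | Counts, provided the death is found | Same; a death outside hospital is not clearly covered by HES as described |
| No PHE test, COVID-19 code in a HES admission | Counts through item 1 | Not stated whether the code establishes infection |
| No PHE test, ICNARC COVID-19 admission | Counts through item 2 | Not stated whether the admission establishes infection |
| No PHE test, no COVID-19 admission, COVID-19 recorded as a cause of death | No stated route; censored at death | No stated route; censored at death |

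The last row is the firm gap. By the protocol's own description, the ONS data would hold these deaths.

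**Step 2: direction and possible size for the death outcome (assumed inputs).** Let s1 and s0 be the shares of COVID-19 deaths captured in exposed and unexposed people. For a rare event with no false positives, and leaving aside non-COVID deaths after infection:

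observed HR = true HR × s1/s0

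The documents give neither share, so every value here is an assumption. With a true HR of 2.0:

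- s1 = 0.9, s0 = 0.9, or 0.7 and 0.7: 2.0 × 1 = 2.00
- s1 = 0.8, s0 = 0.9: 2.0 × 0.889 = 1.78
- s1 = 0.6, s0 = 0.9: 2.0 × 0.667 = 1.33
- s1 = 0.5, s0 = 0.8: 2.0 × 0.625 = 1.25
- s1 = 0.9, s0 = 0.8: 2.0 × 1.125 = 2.25

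Lower capture in the exposed pulls the ratio down, equal capture leaves it unchanged, and the reverse pattern raises it.

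**Step 3: the composite (assumed inputs).** Let d1 and d0 be the shares of composite events that are deaths without a COVID-19 admission. Only these can be lost, so s1 and s0 now refer to capture among them:

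observed HR = true HR × (1 − d1(1 − s1)) / (1 − d0(1 − s0))

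With d1 = 0.20, d0 = 0.05 and a true HR of 2.0:

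- s1 = 0.5, s0 = 0.8: 2.0 × 0.90/0.99 = 1.82
- s1 = 0.6, s0 = 0.9: 2.0 × 0.92/0.995 = 1.85
- s1 = 0.7, s0 = 0.7: 2.0 × 0.94/0.985 = 1.91

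With larger death-only shares, d1 = 0.40 and d0 = 0.10, the same three capture pairs give 1.63, 1.70 and 1.81. With equal death-only shares of 0.10 and equal capture of 0.7 the result is 2.00. Where capture is lower in the exposed, the composite moves less than the death outcome, because admissions enter by other routes. Equal capture leaves the composite exactly unbiased only if the death-only shares are also equal.

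**The case against.** A reader might infer that item 3 requires a documented infection, that RT-PCR is the only accepted proof, and that all COVID-19 deaths in never-tested people are therefore lost. The text does not go that far. Item 3 does not say documented. Data sources names a source for test status, which is not a statement that tests alone establish infection. Items 1 and 2 accept a HES code and an ICNARC admission. Making the RNA-confirmed restriction a sensitivity analysis implies that the main analysis is wider. An untested patient with a coded admission or a COVID-19 ICU stay is already a composite event. The gap is therefore limited to deaths with neither a positive test nor a COVID-19 admission.

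A reader might also infer biased results for care-home residents. None are planned: care-home residence is a category of the domicile covariate. Because the model adjusts for age and domicile, any difference in capture that remains after adjustment may be smaller than the crude difference. The primary exposure is any neuropsychological disease; dementia alone is a secondary analysis.

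Finally, linking ONS COVID-19 deaths suggests an intention to use them. The surviving flow-chart text for Aim 2 lists ONS deaths, and the cohort 1 flow chart and the supplement describing the datasets are not available here. An intention may well exist. Even so, the protocol itself defines this outcome and names its sources, and Data sources assigns mortality to HES. That conflict lies within the protocol and is not a detail left to an analysis plan. Nor does the RNA-confirmed sensitivity analysis help, because it narrows ascertainment and cannot reveal missed deaths.

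**Conclusion.** The point holds in limited form. Three things are firm: item 3 has no rule for establishing infection; Data sources names HES for mortality although ONS COVID-19 deaths are linked; and a COVID-19 death with no positive test and no COVID-19 admission has no stated route into the outcome and is censored. This affects one component of the primary outcome and one secondary outcome, and should be corrected before analysis.

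The bias is conditional. It lowers the death hazard ratio only if capture is poorer in the exposed. That is plausible for dementia, but the documents do not show it. The ranges in the working (2.0 seen as 1.25 to 1.78 for death, and 1.63 to 1.91 for the composite under unequal death-only shares) illustrate the mechanism on assumed inputs. They are not estimates for this study.

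**What to change.** 1. In item 3, also count a death with COVID-19 recorded as a cause in the linked ONS data, with or without a positive test.
2. State that infection for item 3 may also be established by a positive PHE test, a COVID-19 code in HES or an ICNARC COVID-19 admission.
3. Correct Data sources so that ONS, not HES alone, supplies mortality. Because item 3 is all-cause, say whether the ONS extract holds all deaths or only COVID-19 deaths; if only the latter, name the source for other deaths after infection.
4. Report death counts by route (positive test, HES code, ICNARC admission, ONS certification only) and by exposure group.

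The cost is wording, one extra event flag from a dataset already linked, and one table. The downside is that certified but untested deaths are somewhat less specific for COVID-19; the counts by route show how much weight they carry.

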 Cohort one is adult patients aged 18 years of age or over on 24th January 2020 (the study entry date, when the first confirmed COVID-19 case occurred in the UK) who were registered in a primary care practice within the QResearch programme on or before 24th January 2019. Patients will be followed-up from study entry date until development of severe COVID-19 disease, defined as the first date of either hospitalisation, ICU admission, or death. Patients will be censored at the first occurrence of deregistration from the GP practise, death, or date of the final data extract from the linked datasets.

Cohort two is an open cohort of patients aged 18 years of age or over (including those who become 18 within this period) who had been registered with a primary care practise within the QResearch database for at least one year, between 24th January 2015 and 23rd January 2020. For each patient, the earliest day on which all these conditions were met will be defined as their study entry date, and they will be followed-up until development of severe disease due to SARI, defined as hospitalization, ICU admission, or death. Patients will be censored at the earliest of first occurrence of deregistration from the GP practise, death from other causes, 24th January 2020 or date of the final data extract from the linked datasets.

Aim 2.

- Cohort three will include adult patients (aged 18+ on date of hospital admission) discharged alive following a hospital admission including an ICU admission resulting from COVID -19 infection (defined below) between 24 January 2020 and study end date, who were registered in a primary care practice within the QResearch programme before their ICU admission. It will be used to evaluate the risk of subsequent neuropsychological sequalae from the date of discharge. Patients will be censored at the earliest of first occurrence of deregistration from the GP practice, death from other causes, 12 months post discharge from hospital, or date of the final data extract from the linked datasets.

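### The cohort 1 death outcome counts death from any cause at any time after COVID-19 infection, which pulls the hazard ratio towards the exposed group's background mortality ratio and does not match cohort 2

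*Protocol*

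**What the plan says.** Under Definition of outcomes Aim 1, for cohort one, "our primary outcome is the first occurrence of any one of the following": a COVID-19 hospital admission, a COVID-19 ICU admission, or all-"cause mortality following COVID-19 infection". The third item has neither a cause restriction nor a time limit. The hospital item does have a link in time: the positive test must fall "in the 14 days prior to or during a hospital admission period in the HES dataset", unless the admission carries the COVID-19 diagnosis code. Death is then also analysed alone: "Secondary outcomes are each of the three events defined above, considered separately".

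Other parts of the Protocol bear on the same outcome:

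- **Participants, cohort one.** Severe disease is "defined as the first date of either hospitalisation, ICU admission, or death". The same paragraph censors at "deregistration from the GP practise, death, or date of the final data extract". Death without qualification is therefore both an event and a censoring reason.
- **Data linkage.** The linked death file is "Office of National Statistics COVID-19 mortality data, which includes all deaths due to COVID-19 in England", which is cause-specific.
- **Data sources.** Mortality is said to come from HES.
- **Cohort two.** The outcome text lists death with no qualifier, while the Participants section censors deaths from other causes.
- **Statistical Methods, Aim 1.** Follow-up may be capped at one year, but only if hazards prove non-proportional, and follow-up starts at study entry rather than at infection.
- **Sensitivity analyses.** One analysis is restricted to RNA-confirmed cases. It sets no limit on the time to death.

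**The concern.** A patient with a mild infection early in 2020 who dies of something else in 2021 is a severe COVID-19 event under this definition. The exposure groups include dementia, where background mortality may well be raised even after adjustment. The death hazard ratio then mixes two things: the association of neuropsychological disease with dying from COVID-19, and its association with dying at all.

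Adjustment for age and comorbidity does not remove the part of background mortality that belongs to the exposure itself.

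Objective 3 asks whether the association differs between COVID-19 and SARI. If the two cohorts admit different amounts of unrelated mortality, a difference between their hazard ratios may reflect the definitions and not the diseases.

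**Working it through.** The Protocol states no event rate, mortality rate or power figure for this outcome, so there is no figure to reproduce.

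**1. Longest interval.** Cohort 1 runs from 24 January 2020 to 30 June 2021. That is 366 days to 24 January 2021 plus 157 days, or 523 days; 523 / 30.4375 = 17.2 months. This is the extreme, for an infection on the first day.

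**2. Effect on the ratio.** Among infected patients, split the reference-group cumulative hazard into a COVID-19 part and a late background part:

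- Hc = −ln(1 − p0), where p0 is the reference risk of the COVID-19 event
- Hb = m0 × tail / 12, where m0 is reference background mortality per year and tail is the number of months at risk after the acute period
- observed ratio = (HRc × Hc + HRb × Hb) / (Hc + Hb), where HRc and HRb are the exposed-to-unexposed ratios for COVID-19 events and for background death

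The result is a weighted average of HRc and HRb, so it always moves towards HRb.

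All inputs are assumptions: p0 of 10–20% for the composite and 5–8% for death alone, m0 of 2–5% a year, tail of 5–12 months.

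Two worked cases with HRc = 1.0 and HRb = 3.0:

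- Death alone, upper end (p0 5%, m0 5%, 12 months): Hc = 0.0513, Hb = 0.0500; (0.0513 + 0.1500) / 0.1013 = 1.99.
- Composite, lower end (p0 20%, m0 2%, 5 months): Hc = 0.2231, Hb = 0.0083; (0.2231 + 0.0250) / 0.2315 = 1.07.

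Full ranges:

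| HRc | HRb | Composite | Death alone |
|---|---|---|---|
| 1.0 | 3.0 | 1.07–1.64 | 1.18–1.99 |
| 1.5 | 3.0 | 1.55–1.98 | 1.64–2.24 |
| 2.0 | 3.0 | 2.04–2.32 | 2.09–2.49 |
| 2.0 | 2.0 | 2.00 | 2.00 |
| 3.0 | 2.0 | 2.68–2.96 | 2.51–2.91 |

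The composite moves less because it takes the first event only. A late death adds an event only in an infected patient with no earlier COVID-19 hospital or ICU admission. Setting Hb to 0, as a bounded definition aims to do, returns HRc.

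**3. Dependence on the assumed fatality.** Take death alone, equal fatality in both groups (true ratio 1.0), background mortality of 2% against 8% a year, and half a year at risk:

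- fatality 1%: (0.01 + 0.04) / (0.01 + 0.01) = 2.5
- fatality 5%: (0.05 + 0.04) / (0.05 + 0.01) = 1.50
- fatality 10%: (0.10 + 0.04) / (0.10 + 0.01) = 1.27

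The answer depends heavily on a quantity that the Protocol does not give.

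**4. Cohort 1 against cohort 2.** Cohort 1 counts any death after infection as an event. Cohort 2 lists death without qualifier as an event but censors deaths from other causes, which implies SARI-related death. Read that way, cohort 2 leaves unrelated deaths out of the event count and cohort 1 includes them.

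**The case against.** A reader might infer that the rule is bound to inflate the hazard ratio in high-mortality groups. The documents do not support that. The ratio is pulled towards the adjusted background ratio; if COVID-19 carries the larger ratio, the pull is downward (3.0 becomes 2.51–2.91 for death alone). Only the background ratio left after the age spline, care-home residence and comorbidities matters, and the Protocol gives no rates from which to judge it.

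A reader might also carry a figure such as 2.5 over to the primary outcome. That figure is for death alone, at 1% fatality and with unadjusted rates.

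It can further be said that late unrelated deaths may never enter the data, since the Data linkage section describes the ONS file as COVID-19 deaths. That would shrink the problem, but then the all-cause wording in the outcome section is wrong, and the Data sources section names HES instead. The flow diagram for the sequelae study lists all ONS deaths, but that is for Aim 2. The conflict needs resolving whichever source is used.

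All-cause death does avoid errors in certified cause, and a bounded definition will miss some late COVID-19 deaths. That is a good reason to keep the unbounded version as a sensitivity analysis. It is a weaker reason to make it the main definition, given that the hospital component is tied to a test date or a COVID-19 code.

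An analysis plan not shown here might contain a window. The Protocol itself fixes the outcome without one, and its sections disagree about what a death event is.

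**Conclusion.** The point holds as a defect of definition. The cohort 1 death outcome is unbounded in cause and in time, nothing else in the Protocol bounds it, and it does not match cohort 2. The direction of the resulting bias is conditional: upward where the adjusted background mortality ratio exceeds the COVID-19 ratio, which is plausible for dementia but not established by the documents; nil where they are equal; downward where it is lower.

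The effect falls mainly on the secondary death outcome and is diluted in the primary composite. The illustrative ranges rest wholly on assumed rates. They are ratios of cumulative hazards among infected patients, not forecasts of the fitted hazard ratio. The definition should be corrected before analysis.

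**What to change.** 1. Define the cohort 1 death outcome in one of two ways: COVID-19 recorded as a cause on the ONS death record; or death from any cause within a fixed, pre-specified interval of the first positive test (28 and 60 days are examples) or during the COVID-19 admission. Treat other deaths as censoring or competing events.
2. Keep the definition not chosen, and the unbounded one, as sensitivity analyses.
3. Give cohort 2 a matching SARI-related death definition, and make its outcome text agree with its censoring text.
4. Reconcile the Data linkage, Participants, Definition of outcomes and Data sources sections on where deaths come from and which deaths are events or censoring. If the any-cause window is used, confirm that all-cause death dates are available, because the linked ONS file is described as COVID-19 deaths only.

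The cost is mainly wording and some extra analysis. The study is retrospective and would use dates already linked, subject to the check in step 4. The downside is that some late or uncertified COVID-19 deaths drop out of the main analysis; the sensitivity analyses would show how many and whether they matter.

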For cohort two, our primary outcome is the first occurrence of either hospital admission with SARI in the HES dataset (defined as a new ICD-10 code J09-J22 in the HES dataset) or ICU admission in the ICNARC CMP dataset with SARI (defined as any admission with unique diagnostic code any one of RE129 RE131 RE82 RE50 RE86 RE94 RE75 RE133 RE132 RE121 RE1 RE128 RE16 RE130 RE117 RE42 RE41) or death. Secondary outcomes will be each of these three events considered separately (I.e. SARI related hospital admission, ICU admission, death).

Aim 2.

Our primary outcome is development of new neuropsychological disease up to 1 year following hospital discharge which we define as having received a diagnostic code as below:

- Anxiety and stress-related disorders [ICD F40-48 and corresponding Read codes]
- Mood disorders [ICD F30-39 and corresponding Read codes]
- Psychotic disorders [ICD F20-29 and corresponding Read codes]
- Dementia [ICD F00-F03, G30, G31.0 ? and corresponding Read codes]

Secondary outcomes are the diagnosis of new neuropsychological disorders (as defined above) with treatment, and where numbers are available the new diagnosis with or without treatment of each class of disorders, each considered as a separate endpoint.

Neuropsychological treatments are defined as:

- Hypnotics and anxiolytics: (hypnotics, anxiolytics, barbiturates and methyprylone, benzodiazepines)
- Antidepressant drugs (Tricyclic and related antidepressant drugs, Monoamine-oxidase inhibitors, Selective serotonin re-uptake inhibitors, Other antidepressant drugs)
- Drugs used in psychoses and related disorders (Antipsychotic drugs and depot injections, Lithium salts, Phenothiazine derivatives)

Definition of exposures

Aim 1

Neuropsychological disease will be defined as an ordinal variable with the following three categories: no relevant diagnosis or drugs; diagnosis ever recorded without recent drug treatment; diagnosis present with recent drug treatment (with at least two prescriptions for neuropsychological treatments as above within the six months preceding study entry).

Our primary exposure is active neuropsychological disease on the study entry date which we define as having received a diagnostic code as above (24th January 2020 for cohort 1 and 24th January 2015 for cohort 2).

Aim 2.

The primary exposure is a hospital or ICU admission resulting from COVID-19 infection. Comparator exposures are hospital or ICU admission resulting from SARI.

Covariates

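### Cohort 2's primary outcome contradicts itself on death, does not match cohort 1 on either reading, and the named mortality sources conflict, so the Objective 3 comparison is not like for like

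*Protocol*

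**What the plan says.** **Cohort 2, outcome.** Under Definition of outcomes Aim 1, the primary outcome is the first of a SARI hospital admission (HES), a SARI ICU admission (ICNARC codes) or death. The code list ends "RE128 RE16 RE130 RE117 RE42 RE41) or death", with nothing to qualify the last word. The text then runs on into the secondary outcomes, which repeat it: "or death. Secondary outcomes will be each of these three events considered separately (I.e. SARI related hospital admission, ICU admission, death".

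**Cohort 2, follow-up and censoring.** The Participants section says that "they will be followed-up until development of severe disease due to SARI, defined as hospitalization, ICU admission, or death". It then censors at the earliest of deregistration, "death from other causes, 24th January 2020 or date of the final data extract from the linked datasets".

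**Cohort 1.** The death component is all-"cause mortality following COVID-19 infection". The Participants section names death as one of the end events for cohort 1 and, in the next sentence, as a reason for censoring, with no cause attached either time.

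**Mortality source.** Data sources states: "Hospital admission and mortality will come from the HES dataset". Data linkage describes HES as covering people admitted to NHS hospitals and emergency departments. The only death file it links is "Office of National Statistics COVID-19 mortality data, which includes all deaths due to COVID-19 in England". The Aim 2 flow diagram lists all ONS deaths, including for the 2015 to 2020 SARI cohort.

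**Use.** Objective 3 asks whether the risk associated with prior neuropsychological disease differs between COVID-19 and SARI. Statistical Methods, Aim 1 estimates a hazard ratio in each cohort with the same exposures.

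**The concern.** An analyst cannot code the cohort 2 primary outcome from this text, because a death unrelated to respiratory infection is an event in one section and a censoring in another. Whichever section is followed, the death component differs from cohort 1's. Objective 3 sets the two hazard ratios side by side, so a mismatch in definition could be read as a biological difference between COVID-19 and SARI. With about 8.3 million adults in Aim 1, narrow confidence intervals would give no warning of it.

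The source conflict adds to this. As the methods text stands, deaths outside hospital may be visible in cohort 1 when due to COVID-19, while cohort 2 has no named source for them at all.

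**Working it through.** The protocol states no event rate, effect size or power figure for Aim 1, so there is no figure to reproduce. The check is a comparison of sections, followed by an illustration of size.

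**Step 1. How four deaths would be coded, each without a prior qualifying admission.**

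| Death | Outcome definition | Participants section | Source named in the methods text |
|---|---|---|---|
| Cohort 2, cancer, 2017 | Event | Censored | HES only |
| Cohort 2, pneumonia at home, 2018 | Event | Event, if it counts as a SARI death (undefined) | None |
| Cohort 1, positive test, then a non-COVID death at home | Event | Listed both as an end event and as censoring | None |
| Cohort 1, cancer, never infected | Not an event | Listed both as an end event and as censoring | HES only |

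The first and last rows show the asymmetry. Under the outcome definitions, the same type of death is an event in cohort 2 and not in cohort 1.

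**Step 2. Both readings against cohort 1.**
- Outcome definition taken literally: any death (cohort 2) against any-cause death after infection (cohort 1).
- Participants section: SARI-caused death, undefined (cohort 2), against any-cause death after infection (cohort 1).

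Neither pair matches.

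**Step 3. Sources.** A file of COVID-19 deaths holds no deaths from 24 January 2015 to 23 January 2020, and none from other causes after infection. HES, as described, would not be expected to record deaths outside hospital. The methods text for Aim 1 therefore names no source for out-of-hospital deaths in cohort 2, or for non-COVID deaths outside hospital in cohort 1.

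**Step 4. Size, under assumptions.** Let w be the share of the reference group's composite hazard that comes from deaths without SARI, and assume proportional hazards with w constant. Then

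composite HR = (1 − w) × HR_SARI + w × HR_other.

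The documents give none of these inputs. Assumed ranges: HR_SARI 1.2 to 2.0, HR_other 1.0 to 2.5, w 0.1 to 0.5. If other-cause deaths are censored, w = 0 and the result is HR_SARI.

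With HR_SARI = 1.5:

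| HR_other | w = 0.1 | w = 0.3 | w = 0.5 |
|---|---|---|---|
| 1.0 | 1.45 | 1.35 | 1.25 |
| 1.5 | 1.50 | 1.50 | 1.50 |
| 2.5 | 1.60 | 1.80 | 2.00 |

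For example, 0.7 × 1.5 + 0.3 × 2.5 = 1.80.

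Extremes of the range:
- HR_SARI 2.0, HR_other 1.0, w 0.5: 0.5 × 2.0 + 0.5 × 1.0 = 1.50, and 1.50 / 2.0 = 0.75.
- HR_SARI 1.2, HR_other 2.5, w 0.5: 0.5 × 1.2 + 0.5 × 2.5 = 1.85, and 1.85 / 1.2 = 1.54.

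The hazard ratio falls when HR_other is below HR_SARI, rises when it is above, and does not move when they are equal.

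**The case against.** A reader might infer that cohort 2 simply counts every death over five years. The protocol as a whole does not say that. The Participants section ties the event to SARI and censors other-cause deaths, and Statistical Methods speaks of severe SARI outcomes. The bare word may be shorthand: cohort 1's death component, although qualified where it is defined, is also listed plainly as death among the secondary outcomes. In cohort 2's secondary list, the SARI qualifier can be read as governing all three events. This stands, and it makes the finding a contradiction rather than a settled rule. It does not remove the problem, because no section says what a SARI death is and the intended reading still differs from cohort 1.

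A reader might also infer that the study cannot obtain the deaths it needs. The documents do not support that. The Aim 2 flow diagram shows all ONS deaths, the content of the Aim 1 flow diagram is not visible, and the dataset description is deferred to Supplemental material S1, which is not at hand. What can be said is that the sources, as described under Data linkage and Data sources, do not supply these deaths, and that this conflicts with the flow diagram.

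A third tempting inference is that missed out-of-hospital deaths bias the dementia hazard ratio downward. That requires people with dementia to die outside hospital more often than others, and the documents give no place-of-death data. Any such effect would bear mainly on the death-only endpoint. In the first-event composite, a missed death matters only if no qualifying admission came first.

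Finally, Objective 3 does not rest on the composite alone. Hospital and ICU admission are separate secondary outcomes in both cohorts and do not count deaths as events. This limits the damage but leaves the primary outcome unresolved.

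**Conclusion.** The point holds as an internal contradiction in a primary outcome. Death in cohort 2 is unqualified in one section and restricted to SARI in another, SARI death is undefined, and neither version is the counterpart of cohort 1's any-cause death after infection. Cohort 1's own censoring rule also lists unqualified death, although death is one of its outcomes. The mortality sources in the methods text conflict with the Aim 2 flow diagram.

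The size and direction of the effect on Objective 3 are unknown. The factor of 0.75 to 1.54 on the cohort 2 hazard ratio rests wholly on the assumed hazard ratios and on the assumed share of non-SARI deaths. With a 10% share and HR_SARI of 1.5, the hazard ratio moves only between 1.45 and 1.60. The case for correction rests on the text being uncodable and the outcomes unmatched, not on any particular figure.

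**What to change.** 1. **Use the same type of death definition in both cohorts.** There are two workable options:
   - cause-coded death in both, with COVID-19 (cohort 1) or J09–J22 (cohort 2) on the death registration; or
   - death from any cause within the same stated window after a qualifying infection record in both. This needs a definition of SARI outside hospital. SARI is now identified only through HES and ICNARC admissions, which are already events, so a later death would add nothing to a first-event composite. SARI also has no counterpart to the PHE test registry.

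   Certificate-based SARI death in cohort 2 set against any-cause death after infection in cohort 1 would leave the mismatch in place.
2. **Amend Definition of outcomes Aim 1** so that the primary and secondary death outcomes carry the chosen definition in each cohort.
3. **Align the Participants section** so that, in both cohorts, only deaths that are not outcome events are censored.
4. **Name one mortality source** in Data linkage and Data sources: all-cause, cause-coded ONS registrations from 2015 to study end.

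Reporting the ratio of the two hazard ratios with its confidence interval would answer Objective 3 directly, but it is optional and not needed to resolve the contradiction.

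The cost is protocol wording and, if not already held, extension of the ONS linkage from COVID-19 deaths to all deaths, which the Aim 2 flow diagram suggests is already intended.
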